SAE	Serious adverse event
IV	Intravenous
PO	Taken orally
PRN	Taken as needed
TID	Taken three times per day
Q4h	Taken every four hours
CI	Confidence interval
SD	Standard deviation; a parameter which characterizes a population distribution
SE	Standard error
SSI	Surgical Site Injection
ANOVA	analysis of variance; a linear model
NSAID	Non-steroidal anti-inflammatory drug
LOS	Length of Stay

CONFIDENTIAL

This material is the property of the NYU School of Medicine and Langone Medical Center. Do not disclose or use except as authorized in writing by the study sponsor
Interventional Template Version: 28 APR 2017

Protocol Summary

Title	Effects of a Surgical Site Injection on Pain Scores and Narcotic Use after Orthopedic Trauma Surgery
Short Title	Understanding and Improving post-operative Pain in the Fracture Population
Brief Summary	This is a phase I, randomized, single-blind, placebo-controlled, single-center study of the effects of surgical site injection on pain and narcotic utilization in participants who undergo surgery for lower extremity fractures. 400 participants with lower extremity fractures who are admitted for operative fixation will be included in the study. Participants will be randomized to receive either a pain cocktail injection around the fracture site and surrounding tissues or control (no injection). An analysis of pain scores, rehabilitation progress, length of stay, narcotic utilization, and satisfaction scores will be performed.
Phase	Clinical study phase 1
Objectives	To understand the effect of surgical site injections of post-operative pain control
Methodology	phase I, randomized, single-blind, placebo-controlled, single-center study
Endpoint	10mg change in narcotic utilization daily or 15mm change in VAS
Study Duration	4 years
Participant Duration	3 months
Duration of IP administration	Once during surgery
Population	400 participants with peritrochanteric fractures
Study Sites	NYU Langone (Kimmel, Tisch, Langone Orthopedic Hospital, Lutheran)
Number of participants	400
Description of Study Agent/Procedure	Peri-incisional injection of 40cc 0.25% bupivacaine, 5 mg morphine sulfate (1 mg/cc, 5 cc total), and 30 mg of ketorolac (30 mg/cc, 1 cc total) into soft tissue and musculature surrounding the fracture site and 0.25% Marcaine 10 mL into the subcutaneous tissue surrounding the surgical incision.
Reference Therapy	Reference is a control
Key Procedures	Surgical Site injection
Statistical Analysis	As treated analysis will be performed with mean, t-tests, within and between group ANOVA, linear regression, Mann- Whitney-Wilcoxon tests

CONFIDENTIAL

This material is the property of the NYU School of Medicine and Langone Medical Center. Do not disclose or use except as authorized in writing by the study sponsor
Interventional Template Version: 28 APR 2017

1 Key Roles

PI: [name]
Department of Orthopedic Surgery and Cell Biology
NYU Langone Medical Center
[name]
[contact]
[contact]

Co-PI:

[name]
Assistant Professor of Anesthesiology
NYU Langone Orthopedic Hospital
NYU Langone Health
[name]
[name]
[contact]

2 Background and Specific Aims

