2.3 Statistical Hypotheses

We hypothesize that SSI given at the time of surgery will reduce post-operative pain and narcotic usage not only during the patients' inpatient hospital stay but also as an outpatient. Furthermore, SSI will improve post-operative function, shorten length, of stay, and reduce complications not limited to but including deep venous thrombosis, delirium, and narcotic dependency. Failing to reject the null hypothesis would signify that SSI has no clinically relevant impact on post-operative outcomes in hip fracture surgery.

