2.4 Objectives and Purpose

The ultimate goal of this study is to determine how effective SSI is in reducing post-operative pain in patients with lower extremity long bone fractures and to determine how that reduction in post-operative pain impacts a patient's hospital stay in the short term and their use of narcotics during the treatment period. Primary outcomes measures will be reported and observed pain scores and narcotic use. VAS and APS-POQ will be used to measure pain scores. While it is expected that the greatest benefit of the SSI will be seen in the first day or two after surgery it is possible that there will be an overall reduction in long-term narcotic use. Secondarily, function/rehabilitation, length of stay, and complications may be impacted by the intervention.

CONFIDENTIAL

This material is the property of the NYU School of Medicine and Langone Medical Center. Do not disclose or use except as authorized in writing by the study sponsor

Interventional Template Version: 28 APR 2017

3 Study Design and Endpoints

Cohort A: Spinal Anesthesia	ARM 1: Experimental	Sample Size: 100	SSI
	ARM 2: Control	Sample Size: 100	No intervention

Cohort B: General Anesthesia	ARM 1: Experimental	Sample Size: 100	SSI
	ARM 2: Control	Sample Size: 100	No intervention

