3.1 Description of Study Design

The researchers will use NYU admission records, emergency room records, orthopedic consult records, and immediate care records to identify patients eligible for participation in the study. Orthopedic residents and authorized researchers will consent and enroll patients pre-operatively.

Subjects with a qualifying fracture will be randomized to either the SSI or control group. Subjects in the SSI group will receive a peri-incisional injection of 40cc 0.25% bupivacaine (marcaine), 5 mg morphine sulfate (duramorph) (1 mg/cc, 5 cc total), and 30 mg of ketorolac (30 mg/cc, 1 cc total) into soft-tissue and musculature surrounding the fracture site and 0.25% Bupivacaine (Marcaine) 10 mL into the subcutaneous tissue surrounding the surgical incision. The control group will receive no injection. The injection will be administered by the subjects NYU orthopedic surgeon, all of whom are familiar with the technique. The patient will be blinded to if a medication is being injected. Subjects will not receive ketorolac if they have kidney disease or a history of allergy to NSAIDS or aspirin. The dose of ketorolac will be reduced to 15 mg (30 mg/cc, 0.5cc total) in subjects older than 65 years of age, in subjects with a history of peptic ulcer disease, a CrCl of 30 to 50 ml/min, or subjects with diabetes. These modifications are recommended by the manufacturer and are used in standard practice. A sub group analysis will be done on patients who receive this lower dosage to see if it has an impact on the data.

After initial recruitment, subjects' pain will be assessed via visual analog scale (VAS) by nursing staff on a q4h basis. A standardized regimen of pain medication will be given to all subjects who are enrolled. Pre-operatively subjects will receive acetaminophen 1gm oral (every 6-8 hours, not to exceed 4gm daily) and meloxicam 15mg oral once daily. Post-operatively, subjects will receive acetaminophen 1gm oral (every 6-8 hours, not to exceed 4gm daily), ketorolac 30mg injection, once daily in AM, starting POD 1(15mg for patients >65 years of age and/or renal impairment), and pregabalin (Lyrica) 50mg oral every 8 hours (held for sedation). Ice PRN for mild pain, tramadol 50mg oral every 8 hours PRN for moderate pain, and tramadol 100mg oral every 8 hours PRN for severe pain. Oxycodone 5mg oral every 6 hours PRN will be given for breakthrough pain.

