6.2 Analysis of Endpoints

Primary Endpoints:

amount (mg) of narcotics (oral morphine mg equivalents) used
duration of narcotic use
patient reported pain scores

Secondary Endpoints:

length of stay
progress with physical therapy: distance ambulated, range of motion, exercises done
reported long-term narcotic use at home/SAR
discharge location: home, acute rehab, skilled nursing facility
documented narcotic refills
falls
adverse events

The analysis of narcotic Use, VAS, APS-POQ, and SMFA scores will rely on a univariate repeated-measures analysis of variance model for mean score. This model is in the class of models commonly known as a unirep-ANOVA models. It assumes that the mean score is a function of elapsed time and the treatment regimen assigned. This model takes into account the fact that the subject's repeated measures are correlated. The fitted model will provide statistical estimates of the mean levels, the treatment-effect differences between mean levels, the standard deviation, the intra-class correlation coefficient, 95% CIs, standard errors (SE), and statistical hypothesis tests. The estimates of means will be used to compute summary criteria such as area under the curve (AUC) for each regimen. All estimates reported will be presented their 95% CIs.

CONFIDENTIAL

This material is the property of the NYU School of Medicine and Langone Medical Center. Do not disclose or use except as authorized in writing by the study sponsor

Interventional Template Version: 28 APR 2017

All endpoints will be evaluated as fits the data set with graphical figures such as scatter plots, box-and-whisker plots, and frequency histograms to visualize the distribution of these outcomes and their relationships to covariates and treatment assignment. When appropriate descriptive graphical and tabular methods, and Kaplan-Meier curves will also be estimated and presented in a graphical figure.

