6.4 Enrollment/Randomization/Masking Procedures

As per standard of care, an anesthesiologist will determine if subjects receive general or spinal anesthesia. Within these groups subjects will randomized to receive a SSI or no intervention. Randomization will be done via redcapautomated computer randomization. After randomization the surgical team will be informed which group the patient has been randomized into.

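### The Summary endpoint accepts a change in narcotic use or in VAS, with no direction and no condition on the other measure, although opioids are given PRN for pain

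*Combined protocol and SAP*

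**What the plan says.** The only Endpoint entry in the Protocol Summary is "10mg change in narcotic utilization daily or 15mm change in VAS". It gives no sign, no time window and no rule for combining the two parts.

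Other sections bear on the same outcomes:

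- Section 2.3 is directional and joins the two: "We hypothesize that SSI given at the time of surgery will reduce post-operative pain and narcotic usage".
- Section 2.4: "Primary outcomes measures will be reported and observed pain scores and narcotic use". It gives no order and no joint rule.
- Section 6.2 lists three primary endpoints: "amount (mg) of narcotics (oral morphine mg equivalents) used", duration of narcotic use, and patient-reported pain scores. Narcotic use and VAS are each analysed by repeated-measures ANOVA with 95% CIs. There is no joint test.
- Section 3.1 sets the in-hospital opioids: "tramadol 50mg oral every 8 hours PRN for moderate pain, and tramadol 100mg oral every 8 hours PRN for severe pain", and "Oxycodone 5mg oral every 6 hours PRN will be given for breakthrough pain".
- Section 4.8 describes efficacy that could stop the study in terms of lower oral narcotic need. It does not mention pain.
- Section 6.3 sizes the trial on narcotic use alone.

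**The concern.** Under PRN dosing the two outcomes are linked. Pain prompts opioid doses, and opioid doses lower pain. A fall in narcotic use is good news if pain is no worse, and ambiguous if pain has risen. A fall in pain is equally ambiguous if opioid use has risen. The Summary line treats either change as enough, and read literally it does not even require the change to be a reduction.

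This is separate from multiplicity. If narcotic use truly falls and pain truly rises, both findings are real, and alpha control does not remove the conflict. At stake is the headline claim. The stated aim is to reduce both outcomes, and the plan does not say what it will conclude if they move in opposite directions.

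**Working it through.** **Inputs.** The thresholds of 10 mg/day and 15 mm are from the Summary. The narcotic SD of 25 mg, the 15 mg effect, alpha 0.05 and power 0.8 are from Section 6.3. The 100 per arm in each anaesthesia cohort is from the Section 3 table. Section 4.6 expects 300-350 evaluable participants; the lower end gives 300/2 = 150 per arm pooled, or 300/4 = 75 per arm in one cohort if the cohorts fill equally. The documents give no VAS SD and no correlation between the measures. I assume a VAS SD of 20-30 mm and show a range of correlations between the two test statistics. I also assume two-sided 5% tests, because sidedness is not stated.

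**1. The plan's own figure.** n per arm = 2(1.96 + 0.842)²(25/15)² = 43.6, so 44; the t-distribution gives 45. The plan's 90 per group is reproduced as two arms of 45, if a group means one anaesthesia group. For the Summary's 10 mg, n = 2(1.96 + 0.842)²(25/10)² = 98.1, so 99 per arm. At 100 per arm the SE is 25√(2/100) = 3.536 and power is Φ(10/3.536 − 1.96) = 0.81. Pain does not enter this calculation.

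**2. What the line lets through.** Take 100 per arm, a true 10 mg/day fall and a true 10 mm VAS rise, with VAS SD 25.

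- Narcotic use is significantly lower with probability 0.81.
- VAS is significantly worse with probability Φ(10/3.536 − 1.96) = 0.81.
- If the two are independent, both occur with probability 0.807 × 0.807 = 0.65. Simulation over correlations from −0.5 to 0.8 gives 0.70 to 0.62. Widening the VAS SD to 20-30 gives 0.78 to 0.47.
- The chance that either measure shows significant benefit stays at about 0.81 whether the true VAS rise is 5, 10 or 15 mm, because the pain result cannot block it.

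**3. Why a 15 mm margin alone is not enough.** At 150 per arm and SD 25 the SE is 25√(2/150) = 2.887. An observed 8 mm worsening has CI 8 ± 5.66, about 2.3 to 13.7. Pain is significantly worse, yet the CI excludes 15 mm. A true 8 mm worsening passes the margin with probability Φ((15 − 8)/2.887 − 1.96) = 0.68, and a true 5 mm worsening with 0.93. If a CI wholly on the worse side of zero also blocks the claim, these become Φ(1.96 − 8/2.887) = 0.21 and Φ(1.96 − 5/2.887) = 0.59.

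**4. Cost of the condition when the other measure truly does not differ.** The margin part is met with probability Φ(M/(SD√(2/n)) − 1.96). The not-significantly-worse part is met with Φ(1.96) = 0.975. Both parts are upper limits on the same estimate, so the combined probability is the smaller of the two.

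| Condition on the other measure | n per arm | Margin part | Both parts |
|---|---|---|---|
| VAS, M = 15, SD 20 / 25 / 30 | 150 | 1.000 / 0.999 / 0.991 | 0.975 / 0.975 / 0.975 |
| VAS, M = 15, SD 20 / 25 / 30 | 75 | 0.996 / 0.957 / 0.865 | 0.975 / 0.957 / 0.865 |
| Narcotics, M = 10, SD 25 | 150 | 0.934 | 0.934 |
| Narcotics, M = 10, SD 25 | 75 | 0.688 | 0.688 |

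For joint power at 100 per arm with a true 10 mg narcotic effect, the margin part alone gives 0.76-0.81 over VAS SD 20-30 and correlation 0 to 0.5. With both parts and independence it is 0.807 × 0.975 = 0.79 at SD 20 or 25. At SD 30 the margin part binds, Φ(15/4.243 − 1.96) = 0.942, and joint power is 0.807 × 0.942 = 0.76. Simulation at correlation 0.5 gives 0.78-0.80.

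**5. Alpha if either measure may succeed.** Two unadjusted tests give 1 − 0.95² = 0.0975 if independent. Testing each at 0.025 raises the requirement for 10 mg from 99 to 119 per arm (2(2.241 + 0.842)² × 6.25 = 118.8).

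**The case against.** The strongest reply is that the line is labelled an endpoint and is never called a success rule. It may simply record one minimum relevant difference for each outcome. Direction is clear from the background, Aim 1 and Section 2.3. Section 6.2 reports both measures with CIs, so a conflict would be visible. All of this stands. A reader might infer that the plan commits itself to declaring the injection effective when pain worsens, and the documents do not support that. But if the line is not a decision rule, the plan has none for its linked primary outcomes, and the same sentence is needed.

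A reader might also infer that the control and injection arms will be dosed differently, because Section 6.4 says "After randomization the surgical team will be informed which group the patient has been randomized into". That is not shown. The PRN regimen is the same for both arms, the patient is blinded, and nothing says that the nurses who record VAS know the allocation. Nor do the documents say that they are kept unaware, so allocation-influenced dosing is possible but undocumented.

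Finally, whether to require both measures, either one, or one with the other not worse is partly a design choice. That also stands. The request is that the choice be written down and agree with Section 2.3.

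**Conclusion.** The point holds as a gap in interpretation. The Summary line and Section 2.3 do not agree, and no section says how opposite results will be read. Section 4.8 has the same one-measure reading of efficacy. The separate estimates are unaffected.

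The logic needs no numbers. The size figures rest on the assumed VAS SD of 20-30 mm and the assumed correlations, and the 62-70% describes a hypothetical case, not a forecast. The cost of the repair is modest for a narcotic claim on the pooled sample. It is not negligible within one cohort, where the pain condition may be met with probability as low as 0.87 and the narcotic condition with 0.69. Section 6.3 sizes the trial by anaesthesia group, so the within-cohort figures matter.

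**What to change.** In the Summary and Section 6.2:

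1. State both thresholds as reductions, and read narcotic use and VAS over the same named post-operative window.
2. Claim benefit from a reduction in one measure only if the other is neither significantly worse (95% CI wholly on the worse side of zero) nor possibly worse by a pre-stated margin. The sponsor should justify that margin, and it should be no larger than the plan's own 15 mm or 10 mg/day.
3. Otherwise report the two results as a trade-off, not as efficacy.
4. If success on either measure is kept, split or order alpha between the two tests.

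Reconcile the efficacy wording of Section 4.8 with the same reading. Requiring a reduction in both measures, as Section 2.3 implies, is an acceptable alternative.

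The cost is wording plus the power shown above. Margins tighter than 15 mm or 10 mg/day cost more, and an equal alpha split costs about 20 more per arm for a 10 mg effect. No new data are needed, but the text must be fixed before results are seen.

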2.1 Background

Lower extremity fractures comprise the majority of orthopedic surgery emergency room admissions at major medical centers across the country. Whether due to blunt or high energy mechanisms, femur and tibia fractures often necessitate surgical intervention and prolonged hospital stays due to the need for medical clearance, surgery, physical therapy, pain control and discharge planning. Pain management directly impacts a patient's ability to mobilize with physical therapy, their desire to go home or to a rehabilitation facility, and their need for narcotic medications which have deleterious side effects such as delirium and addiction. However, given the unpredictable and "non-elective" nature of fracture care there is little infrastructure in place to optimize outcomes for fracture patients with regards to pain control and its sequela.

A multitude of Level 1 evidence in arthroplasty research has demonstrated that multimodal analgesia pre and post-operatively combined with intra-operative surgical site injection (SSI) leads to reduced post-operative pain, narcotic requirements, and length of stay in addition to increased mobility and patient satisfaction scores¹⁻³. As a result, the standard of practice in arthroplasty has been to use regimented pain protocols including SSI to improve patient outcomes⁴. While pain control is recognized as one of the single most important factors that impacts a patient's hospital stay and outcomes, there is a dearth of Level 1 research on multimodal pain control in the Orthopedic trauma literature.

Recent studies have found support for the use of surgical site injections in patients with femoral fracture treated with plate fixation, intramedullary nail or arthroplasty. In a randomized control trial, Koehler et al studied patients with femur fractures in all anatomic regions and randomly assigned them to either receive a surgical site injection (SSI) and routine pro re nata (PRN) post-op pain medication or only PRN pain medication⁵. Post-operatively, a visual analog score was employed to assess pain and narcotic

CONFIDENTIAL

This material is the property of the NYU School of Medicine and Langone Medical Center. Do not disclose or use except as authorized in writing by the study sponsor
Interventional Template Version: 28 APR 2017

administration which showed a statistically significant difference in pain scores and narcotic usage administration between the two groups on post-operative day one, with those who received SSI having less pain and narcotic usage. What remains to be seen is how these interventions impact rehabilitation and narcotic usage in the long-term.

After sustaining hip or other lower extremity fractures, roughly 50% of patients experience persistent pain at the fracture site. Their perception of this pain and the limitations that they suffer because of it may be influenced by their perioperative pain control and expectations regarding their pain and ability to return to normal living⁶. The goal of this study is to not only impact the acute use of narcotics during the inpatient admission but to impact the long term outcome of fracture pain on long-term functional outcomes for these patients.

At our institution pre-op fracture pain management was not standardized and had been a combination of morphine, fentanyl, dilaudid, and oxycodone given in the emergency and in-patient setting. Post-operatively, oxycodone-acetaminophen 5-325mg and 10-325mg were given for moderate and severe pain every four hours respectively with a dose of oxycodone-acetaminophen 5-325 for breakthrough pain. Adjuncts to these medications such as acetaminophen, tramadol, ketorolac, ofirmev, gabapentin, pregabalin were given inconsistently and often not at all. Starting November 2018 our institution began a new post-op pain medication protocol. In this study a standardized regimen of pain medication will be given to all patients who are enrolled to eliminate this as a potential confounder. The ultimate goal of this study is to diminish the use of post-op narcotics and reduce post-operative pain through the use of an intra-operative SSI.

Rationale for Drug Selection and Route of Administration

In the proposed study, the drugs bupivacaine (marcaine), morphine sulfate (duramorph), and ketorolac (toradol) will be used as a surgical site injection pain "cocktail" as is standard practice in total joint surgery^{1-4,7-10}. Orthopedic pain injection cocktail regimens normally include a local amide anesthetic, a NSAID, and an opiate for multimodal therapy (see table 1, taken from Elmallah et al)¹⁰. Occasionally steroids, antibiotics and other fillers are given. Most commonly ropivacaine or bupivacaine are given as the local anesthetic, morphine sulfate is given as an opiate, and ketorolac is given as the NSAID. Injections are given via tissue infiltration or intramuscular injection and described as "peri-incisional", "periarticular", "extra-articular", and/or "perifracture" injections^{1-4,7-13}. In all cases, the injection is placed in the soft tissue around the relevant zone of injury. In published studies and in common practice, patients receive surgical site injections in the deep tissues including the muscle, synovium, capsule, and periosteum, and into the superficial tissues.

As this replicates the standard of care in arthroplasty, this method of injection to the tissue surrounding the fracture site does not significantly increase risk to subjects. The proposed study follows the same injection methods as Koehler et al. where no adverse events were noted from administration. While there is a potential for inadvertent intra-neural or intravascular injection, the injection will be administered away from blood vessels and nerves and under direct visualization to the soft-tissue surrounding the fracture (predominately muscle) and incision. We do not anticipate patients suffering any major complications from receiving the injection.

As for the choice of drugs, at our institution, a peri-incisional analgesic cocktail is injected before closure of all total hip and knee replacements^{4,9}. This consists of 40ml 0.25% marcaine, 5mg morphine (5ml), and 30 mg ketorolac (1ml). In an RCT, Koehler et al demonstrated the efficacy of a perifracture cocktail containing 400 mg of 0.75% ropivacaine (53.33 mL), 0.6 mg of 1-mg/mL epinephrine (0.6 mL), and 5 mg of 0.5-mg/mL morphine sulfate (10 mL) for pain control in femur fracture patients⁵. In a study by Kang et al., a multimodal periarticular injection was given to hip fracture patients using a 100-mL cocktail of 300 mg ropivacaine (40 mL), 10 mg morphine sulfate (10 mL), 30 mg ketorolac (1 mL), and 300 mg 1:1000 epinephrine (0.3 mL)¹². In a study by Jung et al, multimodal periarticular injections were given for high tibial osteotomies using a 50-

CONFIDENTIAL

This material is the property of the NYU School of Medicine and Langone Medical Center. Do not disclose or use except as authorized in writing by the study sponsor

mL periarticular injection cocktail of 200 mg bupivacaine (20 mL), 10 mg morphine sulfate (10 mL), and 200 mg 1:100,000 epinephrine (0.2 mL)¹³. In a total joint study by Busch, patients received ropivacaine, ketorolac, epimorphine, and epinephrine².

The FDA-approved indications for bupivacaine (marcaine), morphine sulfate (duramorph), and ketorolac (toradol) injection include infiltration and/or intramuscular injection for pain control. Dosing for marcaine infiltration is 0.25% concentration up to 175mg with a further instruction stating "standard textbooks should be consulted to determine the accepted procedures and techniques for the administration of marcaine". Ketorolac tromethamine is approved for intramuscular (IM) administration as: 15 mg in 1 mL (1.5%), 30 mg in 1 mL (3%) , and 60 mg in 2 mL (3%) in sterile solution. Morphine sulfate is approved for intramuscular dosing up to 10mg per 70kg every 4 hours. The peri-incisional injection of these medications is a common prescribed procedure as illustrated in numerous books and studies^{1,7,10-12}.

